4 STUDY POPULATION AND RESTRICTIONS

4.1 Number of subjects and sites

Approximately 66 subjects will be enrolled and randomized, targeting approximately 44 subjects in the treatment group and 22 subjects in the control group. Subjects will be enrolled from up to 3 sites in the United States. Approximately 70% of the total sample size will consist of subjects with a Fitzpatrick skin type of I, II, or III and approximately 30% of the subjects will be Fitzpatrick skin type IV, V, or VI. Subjects from the Fitzpatrick skin type IV, V, and VI group will be distributed as follows: ≥ 6 subjects will be enrolled in the IV Fitzpatrick skin type group and ≥ 12 subjects will be enrolled with Fitzpatrick Skin Types V and VI Fitzpatrick skin type group. Each clinical site will enroll a minimum of 6 subjects with Fitzpatrick skin types IV, V, VI. At least 5 males will be enrolled into the study. Additional information regarding subject enrollment is provided within the sample size justification in [Section 8.1](#).

[figure not shown]
4.2 Inclusion criteria

In order to be eligible for study participation, each subject must meet all of the following criteria:

[figure not shown]
- █ Has right and left IOH volume deficit with a rating of 2 or 3 (moderate or severe) on the [REDACTED] MIHAS.
- █ Has the same MIHAS score on both IOHs (i.e., IOHs are symmetrical).
- █ Is at least 22 years of age.

[figure not shown]
4.3 Exclusion criteria

[figure not shown]
Subjects meeting any of the following criteria are not eligible to participate in the study:

- █ Ever been treated with fat injections or permanent and/or semi-permanent dermal fillers in the midfacial region or plans to receive such treatments during participation in the study.
- █ Received lower eyelid and/or malar region treatments with any absorbable or temporary fillers such as porcine-based collagen fillers, hyaluronic acid (HA) products, RADIESSE®, poly L-lactic acid (PLLA) or received mesotherapy treatment to the area within the past 24 months or plans to receive such treatments during participation in the study.

[figure not shown]

4.4 Subject restrictions during the study

By providing informed consent, subjects commit to refrain from receiving any of the following therapies, procedures, and/or exposures during the study interval (through 13

months for subjects who receive a touch-up, 12 months for treated subjects, or 2 months for control subjects):

4.5 Screen failures

Subjects who sign informed consent but who do not meet eligibility criteria or who withdraw consent prior to being randomized in the electronic randomization system will be defined as screen failures. The investigator will maintain all source documentation for all subjects who are considered screen failures. Minimal information will be collected in the electronic data capture (EDC) system for screen failures, such as date of informed consent, demographics, reason for screen failure.

Individuals who do not initially meet the criteria for participation in this study (screen failure) may be rescreened one time. A subject is eligible for rescreening only if the reason for failure is due to inclusion/exclusion criteria other than his/her MIHAS rating (i.e., baseline MIHAS rating of 0, 1, or 4 or asymmetrical MIHAS scores). Subjects who are screen failures due to MIHAS ratings are not eligible for rescreening.

4.6 Subject withdrawal criteria

A subject may withdraw from the study at any time at his/her own request without prejudice to future medical care. Subjects may also be withdrawn at any time at the discretion of the investigator for safety, compliance, or administrative reasons.

If a subject does not attend a required study visit, the following actions will be taken:

- The site will attempt to contact the subject at least twice and reschedule the missed visit as soon as possible. Every effort to regain contact with the subject will be made (e.g., telephone contact on different dates/times, registered mail). All contact attempts will be documented.
- If attempts to contact the subject are not successful, then the subject will be considered lost to follow up and withdrawn from the study. The reason for early withdrawal will be documented in the case report form (CRF).

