5.1 Schedule of events by visit

The Schedule of Events is presented in [Appendices 10.1](#) (treated subjects) and [10.2](#) (control subjects).

Day 0 (-28 Day) – Baseline Treatment (BT) / No Treatment (Control) includes Screening, Enrollment, and Baseline Assessments

[figure not shown]
The following procedures will be performed at this visit in the following order:

- Obtain written informed consent. A subject must be informed of the study requirements, including the risks and benefits of participation. An IEC/IRB-approved informed consent must be signed and dated by the subject prior to any study related activities or procedures being performed, including discontinuation of any prohibited medications.
- Assign subject identification.
- Collect demographic information.
- Collect height and weight. Height will be collected at the baseline visit only.
- Record medical history.
 - Record ocular history.
- Review and record concomitant medications/therapies.
- Perform urine pregnancy test (if female of childbearing potential). Negative test required prior to randomization.
- Confirm subject meets all eligibility criteria.
 - Treating physician confirms that the subject meets all eligibility criteria prior to randomization.
- Take standardized baseline IOH photographs.
- [REDACTED] perform the MIHAS assessment.

[figure not shown]
- Visual safety assessments on both eyes.
 - Visual acuity test (using a Snellen chart);

- Visual field test;
- Ocular motility exam; and
- Fundoscopic (ophthalmoscopic) view of the eye (not dilated).
- Administer FACE-Q assessments to subject.
- Satisfaction with eyes

- Randomize subject.

NOTE: Subjects randomized to the control group (no treatment) have completed this visit and will be scheduled for the Month 2 visit.

- Injection (for subjects randomized to the treatment group):
 - Administer treatment injection **to first IOH**.
- Wait 30 minutes.
- Perform visual safety assessments on first eye (where IOH area was treated).
- Administer treatment injection to second IOH if treating investigator agrees that it is safe to proceed with injecting the second IOH.
- Wait 30 minutes.
- Perform visual safety assessments on other eye (where second IOH area was treated).
- Dispense subject diary and discuss completion instructions.
- Review and record AEs.
- Schedule 72-hour follow-up phone call and Week 2 visit.

Follow-up Phone call (72-hours ±1 day post treatment)

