5.2.4 *Discontinuation criteria for a subject*

Each subject will be followed to the end of the study, or/if when the sponsor decides to terminate the study, whichever comes first. The only reasons a subject will not be followed for all scheduled visits are withdrawal of consent, lost to follow-up (e.g., moving away from study site; unresponsive to attempts to contact the subject), any AE or adverse device effect (ADE).

If a subject withdraws consent to continue in the study, the investigator should make every attempt to complete the final study visit. If a non-serious AE is unresolved at the time of the subject's final study visit, an effort will be made to follow-up until the AE is resolved or stabilized, the subject is lost to follow-up, or there is some other resolution of this event. The investigator should make every attempt to follow all serious adverse events (SAEs)/unanticipated adverse drug effects (UADEs) to resolution. Information on

pregnancy and the outcome for any woman who becomes pregnant during the study will be collected. Additional information on subject withdrawal criteria is provided in [Section 4.6](#).

5.2.5 *Provision of care for subjects after study discontinuation*

The investigator is responsible for ensuring the adequate and safe medical care of subjects during the study. After completion of the study, the sponsor will follow all applicable local or international regulations and guidelines with regard to follow-up treatment for subjects. The investigator will ensure that appropriate consideration is given to a subject's post-study care.

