6.3 Study treatment

All protocol-specific criteria for the administration of study treatment must be met and documented prior to administration of any study treatment. Study treatment (injection) will be administered only to eligible subjects by a qualified oculoplastic surgeon. Subjects will not be dispensed any investigational material. Any noncompliant subject or site may be discontinued from the study ([Section 5.2](#)).

6.3.1 *Planned treatment procedure and administration*

[figure not shown]
Approximately 44 subjects will be randomized to receive treatment and 22 subjects will serve as the controls. Subjects will be randomized using a 2:1 allocation ratio for treatment to control.

For subjects randomized to the treatment group, both right and left IOHs will receive treatment with Belotero Balance per the administration instructions specified below.

6.3.2 *Infraorbital hollow treatment region*

Belotero Balance is to be deposited in the suprperiosteal plane. Injection volume will be recorded. [Figure 3](#) illustrates the region of the IOH that may be treated. The infraorbital treatment area is at the junction of the lower eyelid and mid-face where a volume deficit has formed. The area is bordered by the nasal sidewall medially, the temporal region of the bony orbit laterally, the bulk of the lower eyelid superiorly, and the superior aspect of the mid-face inferiorly.

Figure 3: Treatment region

6.3.3 *Injection procedure*

6.3.3.1 *Preparation of the injection region*

- Any makeup in the IOH area should be removed.
- As with all transcutaneous procedures, Belotero Balance injection carries a risk of infection and should be conducted with aseptic technique.
- Only topical anesthetic, at the preference of the treating physician, or ice may be applied. Any medication or therapy must be recorded in the CRF.

6.3.3.2 *Directions for use of cannula*

[figure not shown]
1. To attach the cannula to the syringe, open the cannula packaging to expose the hub. Use only the cannula provided with the clinical trial supply.
2. Remove the Luer lock syringe cap from the distal end of the syringe prior to attaching the cannula (see [Figure 4](#)).

Figure 4: Removing the Luer lock syringe cap from the syringe

[figure not shown]

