7.1.1 Primary Effectiveness Endpoint

The primary effectiveness endpoint, the response rate (proportion of subjects with ≥ 1 -grade improvement of both IOHs on the MIHAS from baseline to Month 2) will be summarized as percentages for the treatment ($p_{\text{treatment}}$) (coded with “TreatmentArm”=0) and control (p_{control}) (coded with “TreatmentArm”=1) subjects and inferentially compared according to the following hypothesis:

$$H_0 \text{ (null): } p_{\text{treatment}} \leq p_{\text{control}}$$

$$H_a \text{ (alternate): } p_{\text{treatment}} > p_{\text{control}}$$

For this hypothesis testing, the Fisher’s exact test will be used to compare both response rates in order to test for the superiority of treatment over control. If the left-sided p-value obtained from this test is < 0.025 , H_0 will be rejected in favor of H_a . The following SAS code will be used:

```
proc freq data = dataset;
  tables TreatmentArm*Response /fisher riskdiff(column=2 cl=newcombe) alpha=
                                0.05;
  ods output fishersexact = out pdiffcls=out1;run;
```

Assuming the response is coded with ‘1’ and no response is coded with ‘0’.

Furthermore, a two-sided 95% Newcombe based on Wilson scores confidence interval for the risk difference will be calculated. The primary analysis of the response rates at Month 2 will be based on the ITT, using the observed case (OC) values. The supportive analyses of primary effectiveness endpoint will be for the ITT using imputed (missing imputed as no change) and for the PP using the OC.

Moreover, the response rates for ITT (OC) at Months 2 will be provided for the following subgroups:

- Fitzpatrick Skin Types (I, II, III versus IV, V, VI)
- Gender

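### Protocol 4.6 and 6.3 allow withdrawal for compliance or administrative reasons, which the closed list in 5.2.4 excludes, and no section then requires the Month 2 MIHAS rating

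*Protocol*

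**What the plan says.** Three protocol sections deal with a subject leaving the study early.

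- Section 4.6: "Subjects may also be withdrawn at any time at the discretion of the investigator for safety, compliance, or administrative reasons".
- Section 6.3: "Any noncompliant subject or site may be discontinued from the study". It points to Section 5.2 and does not say who decides.
- Section 5.2.4: "The only reasons a subject will not be followed for all scheduled visits are withdrawal of consent, lost to follow-up", followed by one more item, an adverse event or adverse device effect. The section starts from the default that every subject is followed to the end of the study unless the sponsor stops it. It closes by referring to 4.6 for more on withdrawal.

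Two provisions try to recover assessments from subjects who leave. Section 5.2.4 says: "If a subject withdraws consent to continue in the study, the investigator should make every attempt to complete the final study visit". Section 5.2.1 asks for an effort to perform the scheduled assessments when treatment is stopped during administration and the subject declines to stay.

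On the analysis side, SAP 7.1.1 says: "The primary analysis of the response rates at Month 2 will be based on the ITT, using the observed case (OC) values". It makes the version that imputes missing ratings as no change supportive. Protocol 8.6.1 and SAP 7.4.1.1 put it the other way round: missing primary data are imputed as non-response, and the observed-case analysis is additional.

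**The concern.** Compliance and administrative reasons are grounds for withdrawal in 4.6, and non-compliance is one in 6.3. Neither is in the list in 5.2.4, which is worded as complete. A site cannot tell which rule governs.

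The MIHAS is rated only at baseline and Month 2 (protocol 3.2.1.1 and 8.6.1). A subject withdrawn between the two therefore has no post-baseline value, even when the subject would have been willing to attend. The per-protocol set already deals with major deviations, so non-compliance alone is no reason to give up the rating.

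Such losses could be unequal by arm. One arm is injected and the other is not, so site investigators can infer the arm. The contacts before Month 2 at which compliance with study restrictions is confirmed (72-hour call, Week 2, Month 1) are for treated subjects only. Controls are not seen between baseline and Month 2. Treated subjects are also photographed at Week 2 and Month 1 and checked visually for asymmetry at Month 1. Losses that depend on arm and on visible result are not protected by randomization, and an observed-case test excludes them.

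**Working it through.** **Reading the sections together**

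| Reason for leaving | 4.6 | 6.3 | 5.2.4 | Month 2 rating sought? |
|---|---|---|---|---|
| Consent withdrawn | yes | not addressed | yes | every attempt at a final visit (5.2.4) |
| Lost to follow-up | yes | not addressed | yes | contact attempts (4.6) |
| Safety, AE or ADE | yes | not addressed | yes | only if treatment is stopped during administration (5.2.1) |
| Non-compliance | yes | yes | not listed | no provision |
| Administrative | yes | not addressed | not listed | no provision |

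The conflict is confined to the last two rows. The safety ground in 4.6 largely overlaps the AE/ADE item in 5.2.4.

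**Inputs for the arithmetic**

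- Response rates 0.60 (treatment) and 0.20 (control); 40/20 evaluable and 44/22 enrolled; allowance of up to 10% for missing data, attrition and deviations (protocol 8.1, SAP 4).
- Fisher's exact test, rejecting when the one-sided p is below 0.025 (SAP 7.1.1).
- Assumed, because the documents give no figure: how many subjects are withdrawn on these grounds, and which ones.

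**Formulas**

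For k treated responders of n and c control responders of m, the one-sided p is P(K ≥ k), with K hypergeometric (population n + m, k + c responders in total, n drawn). The rejection probability is the sum over all k and c of Bin(k; 44, p_t) × Bin(c; 22, p_c) × 1{p < 0.025}. To represent withdrawals under the observed-case rule, n is replaced by 44 − min(w, 44 − k), where w is the number of treated non-responders removed.

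**Step 1: the plan's own power figures.** The method gives 79.1% at 40/20 and 84.8% at 44/22, against stated values of about 80% and 84%. They reproduce to within a point.

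**Step 2: losses unrelated to outcome.** Going from 44/22 to 40/20 costs 84.8 − 79.1 = 5.7 percentage points of power and causes no bias.

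**Step 3: a one-sided worst case under the null.** Remove four treated non-responders (4/44 = 9%) and no controls:

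| Common response rate | No removal | Four treated non-responders removed |
|---|---|---|
| 20% | 0.85% | 1.66% |
| 30% | 1.13% | 2.31% |
| 40% | 1.29% | 2.98% |

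With six removed (66 − 60, the whole allowance), the figures are 2.18%, 3.33% and 4.49%.

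**Step 4: proportionate removal.** If the four are matched by two control non-responders, keeping the 2:1 ratio, type I error is 1.26%, 1.46% and 1.48% at the same three rates. It stays below 2.5%.

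**Step 5: the opposite direction.** Losing control non-responders works against the device: 21/44 vs 4/22 gives p = 0.0176, and 21/44 vs 4/20 gives p = 0.0313.

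**Step 6: the imputed rule.** Under protocol 8.6.1 and SAP 7.4.1.1 a withdrawn subject stays in the denominator as a non-responder. Removing treated non-responders then changes nothing, and the first column of Step 3 applies.

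**The case against.** The strongest reply is that the bias arises from SAP 7.1.1. If the primary analysis followed protocol 8.6.1 and SAP 7.4.1.1, withdrawing treated non-responders would gain nothing, whatever the cause of the missing rating. That is right, and the bias should not be counted twice. It does not settle the contradiction between 4.6, 6.3 and 5.2.4, however, and imputation would still replace an obtainable rating with an assumption.

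The sections can also be read as complementary, since 5.2.4 refers to 4.6 and 6.3 refers to 5.2. A cross-reference does not reconcile a list presented as complete with a section that adds to it.

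Opportunity is limited. Treatment is one clinic session with an optional touch-up, so there is no continuing dosing to comply with. No MIHAS or GAIS is scheduled between baseline and Month 2. This stands, and it argues for small numbers. Compliance with study restrictions can still fail, and before Month 2 it is checked in one arm only.

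A reader might infer that the unblinded treating investigator decides who is removed, having seen the result. The documents do not say so. Section 4.6 says only the investigator, 6.3 names nobody, and parts of the blinding text are redacted. What can be said is that the arm can be inferred at the site.

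A reader might also point out that one withdrawal can flip the result: 20/44 vs 4/22 gives p = 0.0264, and 20/43 vs 4/22 gives 0.0224. The arithmetic is correct, but the table was chosen at the boundary. At the planned 60% vs 20%, removing one treated non-responder moves the rejection probability only from 84.8% to 86.3%.

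**Conclusion.** The contradiction is real and stands in legible text. Followed as written, the plan can lose Month 2 ratings that could have been obtained, and the losses may differ by arm. Severity is minor to moderate.

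The documents do not support a claim that type I error will exceed its limit. The Step 3 figures are a bound, not a prediction. They assume that observed cases are primary, that every withdrawal is a treated non-responder, that no control is lost and that no rating is obtained afterwards. Even then, four removals stay below 2.5% at 20%, the control rate that the plan assumes, and at 30%; the limit is passed at 40%. At 20%, six removals also stay below it (2.18%). With proportionate losses there is no breach, and with control losses the bias reverses.

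The trial is a 66-subject pilot with imputed ITT and per-protocol analyses already planned, so sensitivity to a few withdrawals should be visible in the report. Because its results are meant to inform a pivotal design, the wording is still worth correcting.

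**What to change.** Reconcile protocol 4.6, 6.3 and 5.2.4 so that non-compliance or an administrative reason does not by itself end follow-up before the Month 2 assessment. Record a protocol deviation, with exclusion from the per-protocol set if it is major, and still obtain the Month 2 MIHAS and photographs unless consent is withdrawn. Make the list in 5.2.4 agree with the other two sections. Leave the safety ground unchanged; the point concerns data collection, not clinical management.

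Resolve separately which rule for missing data is primary, SAP 7.1.1 or protocol 8.6.1 with SAP 7.4.1.1.

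The cost is a change of protocol wording. The downside is that a few non-compliant subjects stay in the ITT result with their actual ratings and may dilute the effect slightly. The per-protocol analysis would show this.

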5 STUDY PROCEDURES

[figure not shown]
5.1 Schedule of events by visit

The Schedule of Events is presented in [Appendices 10.1](#) (treated subjects) and [10.2](#) (control subjects).

Day 0 (-28 Day) – Baseline Treatment (BT) / No Treatment (Control) includes Screening, Enrollment, and Baseline Assessments

[figure not shown]
The following procedures will be performed at this visit in the following order:

- Obtain written informed consent. A subject must be informed of the study requirements, including the risks and benefits of participation. An IEC/IRB-approved informed consent must be signed and dated by the subject prior to any study related activities or procedures being performed, including discontinuation of any prohibited medications.
- Assign subject identification.
- Collect demographic information.
- Collect height and weight. Height will be collected at the baseline visit only.
- Record medical history.
 - Record ocular history.
- Review and record concomitant medications/therapies.
- Perform urine pregnancy test (if female of childbearing potential). Negative test required prior to randomization.
- Confirm subject meets all eligibility criteria.
 - Treating physician confirms that the subject meets all eligibility criteria prior to randomization.
- Take standardized baseline IOH photographs.
- [REDACTED] perform the MIHAS assessment.

[figure not shown]
- Visual safety assessments on both eyes.
 - Visual acuity test (using a Snellen chart);

- Visual field test;
- Ocular motility exam; and
- Fundoscopic (ophthalmoscopic) view of the eye (not dilated).
- Administer FACE-Q assessments to subject.
- Satisfaction with eyes

- Randomize subject.

NOTE: Subjects randomized to the control group (no treatment) have completed this visit and will be scheduled for the Month 2 visit.

- Injection (for subjects randomized to the treatment group):
 - Administer treatment injection **to first IOH**.
- Wait 30 minutes.
- Perform visual safety assessments on first eye (where IOH area was treated).
- Administer treatment injection to second IOH if treating investigator agrees that it is safe to proceed with injecting the second IOH.
- Wait 30 minutes.
- Perform visual safety assessments on other eye (where second IOH area was treated).
- Dispense subject diary and discuss completion instructions.
- Review and record AEs.
- Schedule 72-hour follow-up phone call and Week 2 visit.

Follow-up Phone call (72-hours ±1 day post treatment)

NOTE: This phone call is only for subjects assigned to the treatment group.

- Review and record changes in concomitant medications/therapies. Confirm subject remains compliant with any applicable study restrictions (see [Section 4.4](#)).
- Review and record AEs. Site staff will review subject diary responses to identify any safety concerns.

- If subject reports a safety concern, the subjects will be scheduled for an unscheduled visit, referred to a specialist, or be provided means of emergency medical care as determined by the investigator.
- Remind subject to continue the diary.
- Schedule and/or confirm Week 2 visit.

Week 2: Day 14 (+3 days)

NOTE: This visit is only for subjects assigned to the treatment group.

- Review and record changes in concomitant medications/therapies. Confirm subject remains compliant with any applicable study restrictions.
- Review subject diary for potential AEs. Remind subject to continue to record in the diary until Month 1 visit.
- Review and record AEs.
- Take standardized IOH photographs.
- Visual Safety Assessments on both eyes.
 - Visual acuity test (using a Snellen chart);
 - Visual field test;
 - Ocular motility exam; and
 - Fundoscopic (ophthalmoscopic) view of the eye (not dilated).
- Schedule and/or confirm Month 1 visit.

Month 1: Day 28 (+3 days) Safety and assessment for Touch-up (TU)

NOTE: This visit is only for treated subjects

- Review and record changes in concomitant medications/therapies. Confirm subject remains compliant with any applicable study restrictions.
- Take standardized IOH photographs.
- Review and collect subject diary. The investigator will review the diary and determine if any diary entries should be recorded as AEs on the AE eCRF.
- Visual Safety Assessments on both eyes.
 - Visual acuity test (using a Snellen chart);
 - Visual field test;

[figure not shown]
- Ocular motility exam; and
- Fundoscopic (ophthalmoscopic) view of the eye (not dilated).
- Review and record AEs.
- Schedule and/or confirm Month 2 visit.
- Asymmetry assessment based on a visual assessment completed by the treating investigator.

NOTE: Subjects who don't receive a touch up to address asymmetry based on the treating investigator's assessment have completed this visit and will be scheduled for the Month 2 visit.

Month 1: Touch-up (TU)

If the treating investigator determines a touch-up is needed to address asymmetry the following procedures will be done:

- Perform urine pregnancy test (if female of childbearing potential and for treated subjects only). Negative test required prior to touch-up injection.
- Injection (only if treating investigator notes asymmetry):
 - Administer touch-up injection **to first IOH.**

- Wait 30 minutes.
- Perform visual safety assessments on first eye (where IOH area was treated).
- Administer treatment injection to second IOH if treating investigator agrees that it is safe to proceed with injecting the second IOH.
- Wait 30 minutes.
- Perform visual safety assessments on other eye (where second IOH area was treated).

NOTE: If only injecting one side, only the side being injected will need the visual safety assessment 30 minutes post treatment.

- Dispense subject diary and discuss completion instructions.

- Review and record AEs.
- Schedule 72-hour follow-up phone call and Week 2 visit.

NOTE: For subjects receiving a touch-up refer to the Follow-up 72 hour Phone Call, Week 2 and Month 1 (safety) assessments as described above. Then subject will continue with Month 2 assessments.

Month 2: Day 56 (+3 days) ALL SUBJECTS

Visit to occur 2 months after last injection (either baseline treatment or touch-up, if applicable) or 2 month after baseline visit for control subjects.

- Review and record changes in concomitant medications/therapies. Confirm subject remains compliant with any applicable study restrictions.
- Perform urine pregnancy test (if female of childbearing potential and for treated subjects only).
- Take standardized IOH photographs.
- Collect weight.
- Review and collect subject diary (touch-up subjects only). The investigator will review the diary and determine if any entries should also be recorded as AEs on the AE eCRF.
- Visual Safety Assessments on both eyes.
 - Visual acuity test (using a Snellen chart);
 - Visual field test;
 - Ocular motility exam; and
 - Fundoscopic (ophthalmoscopic) view of the eye (not dilated).
- [REDACTED] perform MIHAS assessment.

[figure not shown]
- Have the treating investigator complete the investigator GAIS (treated subjects only).

NOTE: Standardized photographs, previously taken during the baseline visit, will be available for the treating investigator to reference when completing the Month 2 GAIS assessment.

- Have subjects complete the subject GAIS (treated subjects only).

NOTE: Standardized photographs, previously taken during the baseline visit, will be available for the subject to reference when completing his/her Month 2 GAIS assessment.

- Administer FACE-Q assessments to subject.
 - Satisfaction with eyes

- Review and record AEs.
- Schedule and/or confirm Month 3 visit (treated and touch-up subjects only).

Note: This is the last visit for subjects assigned to the control group.

Month 3 (Day 84), 6 (Day 168), 9 (Day 252), and 12 (Day 336) (± 7 days)

- Review and record changes in concomitant medications/therapies. Confirm subject remains compliant with any applicable study restrictions.
- Take standardized IOH photographs.
- Visual Safety Assessments on both eyes.
 - Visual acuity test (using a Snellen chart);
 - Visual field test;
 - Ocular motility exam; and
 - Fundoscopic (ophthalmoscopic) view of the eye (not dilated).
- Review and record AEs.
- Schedule and/or confirm the next visit. Study participation ends after Month 12 visit.

5.1.1 *Scheduled visits*

All scheduled visits and applicable study assessments must occur as noted in [Sections 5.1](#) and the Schedule of Events ([Appendices 10.1](#) (treated subjects) and [10.2](#) (control subjects)).

5.1.2 *Unscheduled visits*

To ensure subject safety during the study, any subject who requires additional follow-up during the study for any reasons (that does not fall on a scheduled study visit) should

have that visit recorded as an unscheduled visit and all applicable CRFs for that unscheduled visit completed. Treated subjects will be followed at 72 hours via a safety follow up phone call. These phone calls may result in an unscheduled visit if any safety concerns are identified. Treated subjects will be completing a diary for 28 days post baseline injection and for 28 days post touch-up injection, which may alert site staff to schedule an unscheduled visit if any safety concerns are identified.

